6. DOSE MODIFICATION/TOXICITY MANAGEMENT

A number of measures will be taken to ensure the safety of patients participating in this study. These measures will be addressed through exclusion criteria (see Section 3.2) and routine monitoring as follows.

Patients enrolled in this study will be evaluated clinically and with standard laboratory tests before and during their participation in this study. Safety

evaluations will consist of medical interviews, recording of adverse events, physical examinations, blood pressure, and laboratory measurements. Subjects will be evaluated for adverse events (all grades for phase I section; for phase II portion of study; and all grades for non-hematologic events, grade 3 and 4 only for laboratory abnormalities.), serious adverse events, and adverse events requiring study drug interruption or discontinuation at each study visit for the duration of their participation in the study.

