11.1.2 Phase II

The primary objective for the phase II part is to further evaluate the safety and efficacy of lenalidomide when given in combination with obinutuzumab at the MTD of lenalidomide determined in phase I. The maximum number of patients that will be recruited for the phase II part is 60 (include additional 54 and the 6 patients treated at the MTD in phase I) with 30 for each of the two patient cohorts: the patients with follicular lymphoma (grade 1-3a) and the patients with either follicular lymphoma, marginal zone lymphoma or SLL. The patients who are treated at the MTD in the phase I part will be included in phase II (in relevant cohort). The objective response (complete response + partial response) after 6 cycles and DLT after 1 cycle will be monitored simultaneously using the Bayesian approach of Thall, Simon, Estey (1995, 1996) as extended by Thall and Sung (1998).

Cohort A: Patients with Follicular lymphoma

Historical data on 43 patients (Witzig, 2009) with relapsed or refractory indolent non-Hodgkin's lymphoma treated with lenalidomide show an objective response (OR) rate of 23% and DLT rate of under 30%. Independence was assumed between OR and DLT. It is expected for the current trial that the two-drug combination will improve the OR rate by 20% to 43% while the DLT rate is maintained at or below 30%. A sample size of 30 patients ensures that, if the trial is not terminated early, a posterior 90% credible interval for OR rate will have width of 0.283 at most, under the assumption of a 43% of OR rate. We will claim that the regimen is worth of further investigation if the lower limit of the posterior 90% credible interval for OR rate is higher than 0.23. The probabilities of OR and DLT for the historical data are modeled by beta distributions (*Beta* (9.89, 33.11) and *Beta* (12.9, 30.1), respectively). The prior probabilities of OR and DLT for the experimental regimen are also modeled by beta distributions (*Beta* (0.46, 1.54) and *Beta* (0.6, 1.4), respectively), which have the same *means* as the corresponding beta distributions for the historical data.

Denoting the historical probabilities of objective response rate and DLT rate by $\{p(\text{OR}, \text{H}), p(\text{DLT}, \text{H})\}$, the following decision criteria will be applied:

- 1) Let E correspond to the experimental treatment, stop if

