11.2 Analysis Plans

Phase I:

Toxicity type and severity by dose level will be summarized using frequency tables.

Phase II:

The analysis for phase II will include the patients who are treated at the MTD in phase I.

Toxicity type and severity will be summarized for each patient cohort using frequency tables.

Summary statistics will be provided for continuous variables. Frequency tables will be used to summarize categorical variables. The overall response rate for each patient cohort will be calculated and the Clopper Pearson confidence interval will be provided. Chi square test or Fisher's exact test will be used to evaluate the association between patient prognostic factor and response. The distribution of time-to-event endpoints including overall survival and progression free survival will be estimated using the method of Kaplan and Meier.

Comparison of time-to-event endpoints by important subgroups will be made using the log-rank test.

For the toxicity endpoint, per-treated analysis will be performed to include any patient who received the treatment regardless of the eligibility nor the duration or dose of the treatment received. For the efficacy endpoints, intend-to-treat analysis will be applied to the eligible patients.

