12.2.1 ADVERSE EVENT REPORTING PERIOD

The study period during which all AEs and SAEs must be reported begins after the first protocol intervention, and ends 30 days following the last administration of study treatment or study discontinuation/termination, whichever is earlier. After this period, investigators should only report SAEs that are attributed to prior study treatment.

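### Pooled phase II toxicity tables mix all-grade with grade 3–4-only laboratory recording, so grade 1–2 blood-count rates would be substantially understated

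*Combined protocol and SAP*

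**What the plan says.** Section 6 sets the recording rule in one parenthesis. It opens "all grades for phase I section; for phase II portion of study" and continues, after a semicolon, "all grades for non-hematologic events, grade 3 and 4 only for laboratory abnormalities". The same sentence then adds serious events and events that lead to interrupting or stopping study drug, with no grade limit.

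Section 11.2 pools the two phases: "The analysis for phase II will include the patients who are treated at the MTD in phase I". It promises that "Toxicity type and severity will be summarized for each patient cohort using frequency tables". For toxicity, "per-treated analysis will be performed to include any patient who received the treatment regardless of the eligibility". Nothing there limits laboratory rows to grade 3 or higher, splits them by phase of enrolment or changes the denominator.

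Section 11.1.2 gives the mix: "60 (include additional 54 and the 6 patients treated at the MTD in phase I", "with 30 for each of the two patient cohorts", with the carried-over patients placed in whichever cohort is relevant. Section 3.2 keeps SLL/CLL patients out of phase I.

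Section 12.2.1 is broader than section 6: "The study period during which all AEs and SAEs must be reported begins after the first protocol intervention". Section 12.2.2 includes events found by laboratory test. Neither sets a grade threshold or distinguishes the phases.

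**The concern.** A severity table is interpretable only if every patient in the denominator was observed under the rule that defines the numerator. For grade 1–2 laboratory abnormalities that fails here: a few patients are recorded at all grades and the rest, in the main, are not. A reader of the pooled table could not tell an abnormality that did not occur from one that was not recorded. The two cohorts could also appear to differ merely because they contain different numbers of phase I patients.

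Safety is the first-listed phase II primary objective (section 2.2.1), and treatment can run to 30 months, so low-grade cytopenias are part of what the tables should describe.

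The rule is also ambiguous. A grade 2 rise in creatinine or a transaminase is a non-hematologic event (all grades) and also a laboratory abnormality (grades 3–4 only). Staff could reasonably record it or omit it.

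**Working it through.** **Patient counts.** Phase II: 54 new + 6 from phase I = 60 = 2 × 30. Study maximum: 18 + 60 − 6 = 72. Both reproduce the plan's figures. Section 11.1.1 defines the MTD by a level at which 6 patients were treated, which agrees with the 6 carried over.

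**Which clause belongs to which phase.** The punctuation in section 6 is poor. However, all grades and grades 3–4 only cannot both govern laboratory events in phase I. Assigning the restriction to phase II is the only reading that gives both halves a meaning.

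**Formula.** Let q be the true proportion of patients with a grade 1–2 laboratory event of a given type, k the number of phase I patients among a cohort's 30 (0 to 6), and r the share of such phase II events captured by another route. Then:

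- expected displayed rate = q × [k + (30 − k) × r] / 30
- with r near 0, this is about q × k/30, and the relative shortfall is 1 − k/30
- with r = 1, the displayed rate equals q

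**Inputs.** The 30 and the 6 come from section 11.1.2. Neither q nor r is in the documents. I take q from 20% to 80% as an assumption and set r = 0 for the table.

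| k | k/30 | q = 20% | q = 40% | q = 60% | q = 80% |
|---|---|---|---|---|---|
| 6 | 20% | 4% | 8% | 12% | 16% |
| 3 | 10% | 2% | 4% | 6% | 8% |
| 0 | 0% | 0% | 0% | 0% | 0% |

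The relative shortfall is 80% at k = 6, 90% at k = 3 and 100% at k = 0. Across both cohorts, 6/60 = 10% of patients are recorded at all grades.

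**Example.** With q = 50% and k = 6, expect 6 × 0.5 = 3 recorded events. Shown over the cohort this is 3/30 = 10% (Clopper–Pearson 95% interval 2% to 27%), which excludes the true 50%. Over the patients actually observed at all grades it is 3/6 = 50% (12% to 88%).

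**Is r small for blood counts?** The written dosing rules suggest so. Table 5 calls for no delay at grade 1–2 hematologic toxicity. Table 8 acts on neutropenia only at grade 4 or at grade 3 with fever, and on thrombocytopenia from grade 3 (below 50,000). The platelet level for starting a new cycle in section 6.2.2 is the same 50,000. What remains is mainly the discretionary hold in section 6.1.6 and serious events.

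**The case against.** The strongest objection is that phase II patients are not barred from contributing low-grade laboratory events. Section 6 separately captures serious events and those leading to interruption or discontinuation. Section 6.1.6 allows either drug to be held at discretion with no grade threshold. Table 8 has lenalidomide omitted for thyroid abnormalities with no grade stated. The special-interest list in section 12.3.2 includes tumor lysis syndrome at all grades and raised transaminases with raised bilirubin or jaundice. This stands. A reader might infer that only phase I patients can contribute, that 20% is a hard ceiling in any cohort, or that SLL patients must show exactly zero. The documents do not support those statements; the table above is the r = 0 case.

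Second, chemistry values may fall under the all-grades half of the rule, in which case nothing is lost for them. This also stands: the arithmetic applies with confidence only to blood counts.

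Third, sections 12.2.1 and 12.2.2 could be taken to govern, so that everything is recorded in both phases. But a general reporting clause with no grade or phase terms does not clearly displace a specific one. The conflict itself needs resolving.

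Fourth, section 11.2 does not explicitly call for grade 1–2 laboratory rows. A grade 3–4 display would comply and would remove the problem. True, but a table of type and severity with no restriction naturally includes them.

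Finally, recording only grade 3–4 laboratory events in phase II is a legitimate choice. The defect is combining it with all-grade data unannounced.

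**Conclusion.** The point holds as a safety-reporting defect. If section 6 is followed as best read and the pooled tables show grade 1–2 hematologic laboratory rows over all treated patients, the displayed rates fall about 80% to 100% below the true ones, depending on k, less whatever the other capture routes recover. For non-hematologic laboratory values the effect depends on which half of the section 6 rule applies.

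A reader might go further and conclude that the trial's safety decisions are compromised. They are not. DLT and MTD rules, both stopping boundaries and the ORR criterion do not count grade 1–2 laboratory events, and grade 3–4 rates are recorded alike in both phases. Nor are the underlying data lost, since hematology and chemistry are scheduled for every patient in section 2.1.

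The size rests on assumed true rates, on r being small for blood counts, and on an allocation of the six patients that the plan leaves open.

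**What to change.** In section 11.2, choose one of two options:

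- Show laboratory toxicity in the pooled phase II cohort tables at grade 3 or higher only, for everyone including the carried-over patients, and keep grade 1–2 laboratory events to the phase I by-dose tables. This costs only wording, but leaves low-grade laboratory events out of the phase II tables.
- Derive all laboratory grades for every patient from the scheduled CBC and chemistry values. This keeps the low-grade information and needs some programming, but no new visits or samples.

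Restricting the denominator to patients recorded at all grades would remove the bias, but would leave at most six patients in the whole trial.

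Under either option, repunctuate the rule in section 6, state whether non-hematologic laboratory values follow its all-grades or its grade 3–4 half, and cross-refer to it from section 12.2.1 so that sections 6, 12.2.1 and 12.2.2 agree.

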6.1 OBINUTUZUMAB

The dose of obinutuzumab generally remains constant throughout the trial. Obinutuzumab infusion should be interrupted for severe reactions, e.g., rapid tumor lysis. Treatment of infusion-related symptoms with diphenhydramine and acetaminophen is recommended. Additional treatment with bronchodilators or IV saline may be indicated. Epinephrine, antihistamines, and corticosteroids should be available for immediate use in the event of a hypersensitivity reaction to obinutuzumab (e.g., anaphylaxis). In most cases, the infusion must be resumed at no greater than 50% of initial rate (e.g., from 100mg/hr to 50mg/hr) when symptoms and laboratory abnormalities have completely resolved. Obinutuzumab can be resumed on the following day if infusion reaction prevented full delivery on day 1.

Infusions should be discontinued in the event of serious or life-threatening cardiac arrhythmias. Subjects who develop clinically significant arrhythmias should undergo cardiac monitoring during and after subsequent infusions.

Carriers of hepatitis B and patients with a history of hepatitis B infection or positive serology should be excluded from clinical trials except in situations where the potential benefit is determined to justify the risk of possible hepatitis B reactivation, which can be fatal. Patients with positive serology should have viral DNA levels checked and a gastrointestinal consultation obtained. If treated with obinutuzumab, such patients should be closely monitored for clinical and laboratory signs of active HBV infection and for signs of hepatitis throughout their study participation.

6.1.1 MANAGEMENT OF INFUSION-RELATED REACTIONS AND ANAPHYLAXIS

Medications (including epinephrine for subcutaneous injections, corticosteroids, diphenhydramine hydrochloride for IV injection) and resuscitation equipment should be available for immediate use at point of infusion. Management of infusion-related symptoms for obinutuzumab is summarized in Table 4. In the event of a life-threatening IRR (which may include pulmonary or cardiac events) or an IgE-mediated anaphylactic reaction, obinutuzumab should be discontinued and no additional drug should be administered. Patients who experience any of these reactions should receive aggressive symptomatic treatment and will be discontinued from study treatment.

Patients who experience obinutuzumab -associated, infusion-related temperature elevations of $>38.5^{\circ}\text{C}$ or other minor infusion-related symptoms may be treated symptomatically with acetaminophen (≥ 500 mg) and/or H₁- and H₂-histamine–receptor antagonists (e.g., diphenhydramine hydrochloride, ranitidine). Serious infusion-related events, manifested by dyspnea, hypotension, wheezing, bronchospasm, tachycardia, reduced oxygen saturation, or respiratory distress, should be managed with additional supportive therapies (e.g., supplemental oxygen, β_2 -agonists, epinephrine, and/or corticosteroids) as clinically indicated according to standard clinical practice.

Table 4

Guidelines for Management of Infusion-Related Symptoms Related to Obinutuzumab

Infusion-Related Symptoms ^a	Guidance
Grade 4	
 Discontinue infusion immediately, treat symptoms aggressively, and do not resume treatment.
Grade 3	
 Hold infusion. Give supportive treatment.^b Upon symptom resolution, may resume infusion rate escalation at the investigator's discretion.^c If the same adverse event recurs with the same severity, treatment must be permanently discontinued.
Grade 1–2	
 Slow or hold infusion. Give supportive treatment.^b Upon symptom resolution, may resume infusion rate escalation at the investigator's discretion.^c

^a Refer to National Cancer Institute Common Terminology Criteria for Adverse Events, Version 4.0 for the grading of symptoms. This table does not refer to management of immunoglobulin E-mediated allergic reactions, which should be managed as directed in Section 6.1.1.

^b Supportive treatment: Patients should be treated with acetaminophen and an antihistamine such as diphenhydramine hydrochloride if they have not been received in the last 4 hours. Intravenous saline may be indicated. For bronchospasm, urticaria, or dyspnea, patients may require antihistamines, oxygen, corticosteroids (e.g., 100 mg of intravenous prednisolone or equivalent), and/or bronchodilators. For hypotension, patients may require vasopressors.

^c Escalation of the infusion rate after re-initiation: Upon complete resolution of symptoms, the infusion may be resumed at 50% of the rate achieved prior to interruption. In the absence of infusion-related symptoms, the rate of infusion may be escalated in increments of 50 mg/hr every 30 minutes to a maximum rate of 400 mg/hr.

6.1.2 MANAGEMENT OF TUMOR LYYSIS SYNDROME

For patients with evidence of TLS, obinutuzumab should be discontinued and the patients treated as clinically indicated. Following the complete resolution of TLS complications, obinutuzumab may be re-administered at the full dose during the next infusion in conjunction with prophylactic therapy as indicated (see Section 5.1.3.2).

6.1.3 CARDIOTOXICITY

Infusions should be discontinued in the event of serious or life-threatening cardiac arrhythmias. Patients who develop clinically significant arrhythmias should undergo cardiac monitoring during and after subsequent infusion of obinutuzumab. Patients with preexisting cardiac conditions, including arrhythmias and angina, who have had recurrences of these events during obinutuzumab therapy should be monitored throughout the infusion and immediate post-infusion period.

6.1.4 HEPATITIS B VIRUS REACTIVATION

Patients with a history of hepatitis B infection will be excluded from study.

6.1.5 DOSAGE MODIFICATION DURING MAINTENANCE THERAPY WITH OBINUTUZUMAB

6.1.5.1 Nonhematologic Toxicities

For Grade ≥ 2 nonhematologic toxicities related to obinutuzumab, treatment with obinutuzumab will be delayed for a maximum of 3 weeks until resolution to Grade ≤ 1 or baseline (see Table 4). Resumption of dosing without complete resolution of toxicity may be considered only upon careful weighing of the risks and benefits to the patient by the investigator. It is recommended that cycles be delayed in 1 week increments. If treatment is delayed for more than 3 weeks, study treatment will be discontinued.

There will be no dose reductions of obinutuzumab.

6.1.5.2 Hematologic Toxicity

Note that lymphopenia is not considered to be a hematologic toxicity, because it is an expected outcome of therapy.

For Grade ≥ 3 hematologic toxicities (defined as neutropenia, anemia, or thrombocytopenia), treatment with obinutuzumab will be delayed for a maximum of 3 weeks until resolution to Grade ≤ 2 (see Table 5). Resumption of dosing without complete resolution of toxicity may be considered only upon careful weighing of the risks and benefits to the patient by the investigator. It is recommended that cycles be delayed in 1-week increments. If treatment is delayed for more than 3 weeks, study treatment will be discontinued.

There will be no dose reductions of obinutuzumab.

Table 5
Guidelines for Dose Delay or Modification of Obinutuzumab
during Maintenance Therapy

Event	Dose Delay or Modification
Grade 2, 3, or 4 nonhematologic toxicity ^a	
 Delay doses of obinutuzumab for a maximum of 3 weeks. If improvement to Grade ≤ 1 or baseline, administer full dose of obinutuzumab.
Grade 1 nonhematologic toxicity ^a	
 No dose reduction or delay.
Grade 3 or 4 hematologic toxicity	
 Delay doses of obinutuzumab for a maximum of 3 weeks. Administer myeloid growth factors for neutropenia. Administer RBCs or platelets as required. If improvement to Grade ≤ 2, administer full dose of obinutuzumab.
Grade 1 or 2 hematologic toxicity	
 No dose reduction or delay.

RBC = red blood cell.

^a For tumor lysis syndrome or hepatitis B virus reactivation, Section 6.1.2 or 6.1.4, respectively.

^b Dose delays and interruptions will only occur if toxicity is felt to be related to obinutuzumab per the investigator or treating physician.

6.1.6 Dosage Modification During combination Therapy

For Grade ≥ 3 nonhematologic toxicities felt to be related to obinutuzumab by the investigator or treating physician, treatment with obinutuzumab will be delayed until resolution to Grade ≤ 1 or baseline. Resumption of dosing without complete resolution of toxicity may be considered only upon careful weighing of the risks and benefits to the patient by the investigator.

For Grade ≥ 3 hematologic toxicities (defined as neutropenia, anemia, or thrombocytopenia), treatment with obinutuzumab will be delayed until resolution to Grade ≤ 2 . Resumption of dosing without complete resolution of toxicity may be considered only upon careful weighing of the risks and benefits to the patient by the investigator.

Note that lymphopenia is not considered to be a hematologic toxicity, because it is an expected outcome of therapy.

There will be no dose reductions of obinutuzumab.

If a toxicity, hematologic or non-hematologic is felt to be due to either lenalidomide or obinutuzumab, patients safety is considered paramount and either drug can be held at the investigator or treating physicians discretion until the investigator or treating physician feel the causal agent can be restarted safely. In cases of medication hold per physician, redosing must meet all criteria for restarting new cycle (section 6.2.2).

6.2 DOSE MODIFICATION: LENALIDOMIDE

Subjects will be evaluated for AEs at each visit with the NCI CTCAE v4.0, see below for full instruction on initiation of a new cycle of therapy and dose modifications during a cycle of therapy.

Table 6, 7 Lenalidomide dose adjustment steps

Table 6: LENALIDOMIDE Dose Adjustment Steps	
Starting Dose	MTD mg daily for 21 days every 28 days
Dose Level -1	MTD -5 mg daily for 21 days every 28 days
Dose Level -2	MTD -10 mg daily for 21 days every 28 days
Dose Level -3	MTD-15 mg daily for 21 days every 28 days

Table 7: LENALIDOMIDE Dose Adjustment Steps in SLL	
Starting Dose	MTD or max of 10 mg daily for 21 days every 28 days
Dose level +1	Starting dose +5 mg daily for 21 days every 28 days
Dose level +2	Starting dose +10mg daily for 21 days every 28 days
Dose level +3	Starting dose +15mg daily for 21 days every 28 days
Dose level -1	Starting dose -5 mg daily for 21 days every 28 days
Dose level -2	Starting dose -10 mg daily for 21 days every 28 days
Dose level -3	Starting dose -15mg daily for 21 days every 28 days

The minimum dose level is 15mg below MTD or 5mg daily for 21 days, (whichever is higher).

Patients who cannot tolerate or require dose reduction below 5mg daily lenalidomide will not receive further doses of lenalidomide.

If the patient is attaining clinical benefit in the opinion of the treating physician, and has attained at least a partial response, obinutuzumab dosing will continue per study design to a maximum of 21 doses.

The starting dose will be predefined during the phase I portion of the study based upon cohort (see Table 2). In the phase II portion of the study, the starting dose will be the maximum tolerated dose as defined by phase I portion.

6.2.1 INSTRUCTIONS FOR LENALIDOMIDE DOSE MODIFICATIONS OR INTERRUPTION DURING A CYCLE.

Table 8: Dose Modification for Lenalidomide		
NCI CTC Toxicity Grade	Day 2-14 of Cycle	≥Day 15 of Cycle
Grade 3 neutropenia associated with fever (temperature $\geq 38.5^{\circ} \text{C}$) or Grade 4 neutropenia	
 • Hold (interrupt dose). • Follow CBC weekly. • If neutropenia has resolved to \leq grade 2 restart at next lower dose level and continue the cycle until Day 21. 	
 • Omit lenalidomide for remainder of cycle 
If neutropenia is the only toxicity for which a dose reduction is required. G-CSF may be used and the dose maintained for the next cycle at the investigators discretion.

Thrombocytopenia \geqGrade 3 (platelet count $< 50,000/\text{mm}^3$)	
 • Hold (interrupt dose). • Follow CBC weekly. • If thrombocytopenia resolves to \leq grade 2 restart at next lower dose level and continue the cycle until Day 21. 	
 • Omit lenalidomide for remainder of cycle
Erythema multiforme \geq Grade 3	
 • Discontinue lenalidomide study drug. 	
 • Discontinue lenalidomide study drug.

2013-0261 - Obinutuzumab Plus Lenalidomide in Low Grade Lymphoma

			Dose
Sinus bradycardia/ other cardiac arrhythmia Grade 2	
 Hold (interrupt) dose. Follow at least weekly. If the toxicity resolves to ≤ grade 1 prior to Day 21 restart at next lower dose level and continue the cycle until Day 21. 	
 Omit lenalidomide for the remainder of the cycle. 	
≥ Grade 3	
 Discontinue lenalidomide study drug. 	
 Discontinue lenalidomide study drug. 	
Allergic reaction or hypersensitivity Grade 2-3	
 Hold (interrupt) dose. Follow at least weekly. If the toxicity resolves to ≤ grade 1 prior to Day 21 restart at next lower dose level and continue the cycle until Day 21. 	
 Omit lenalidomide for the remainder of the cycle. 	
Grade 4	
 Discontinue lenalidomide study drug. 	
 Discontinue lenalidomide study drug 	
Venous thrombosis/embolism ≥ Grade 3	
 Hold (interrupt) dose and start anticoagulation; restart at investigator's discretion (maintain dose level). 	
 Omit lenalidomide for remainder of cycle. Anticoagulation measures as described in Concomitant therapy section below. 	
other non-hematologic toxicity assessed as Lenalidomide-related ≥ Grade 3	
 Hold (interrupt) dose. Follow at least weekly. If the toxicity resolves to ≤ grade 2 prior to Day 21 restart at next lower dose level and continue the cycle until Day 21. 	
 Omit lenalidomide for remainder of cycle. Initiate appropriate supportive care, restart lenalidomide next cycle (decrease by one dose level) 	
Hyperthyroidism or hypothyroidism	
 Omit lenalidomide for remainder of cycle. evaluate etiology, and initiate appropriate therapy. Restart lenalidomide next cycle (decrease dose by one dose level). 	
 Omit lenalidomide for remainder of cycle evaluate etiology, and initiate appropriate therapy. Restart lenalidomide next cycle (decrease dose by one dose level). 	

adjustments/intervention: lenalidomide associated rash:

Grade

1-2

Day 2-14 of Cycle

- Start supportive

Day ≥ 15 of Cycle

- Start supportive

2013-0261 - Obinutuzumab Plus Lenalidomide in Low Grade Lymphoma

	measures if grade 2	measures if grade 2
Non-blistering rash	
• No dose adjustment• Hold (interrupt) dose.• Startsupportive measures.• Evaluate weekly• If rash resolves to ≤ grade 1 prior to day 21 restart at dose level -1 and continue to Day 21.• Restart next cycle at dose level -1.	
• No dose adjustment• Omit lenalidomide for remainder of cycle.• Startsupportive measures.• Evaluate weekly until rash ≤ grade 1.• Restart next cycle at dose level -1.
Grade 3		
Grade 4*	
• Discontinue lenalidomide• Dermatology evaluation• Startsupportive measures	
• Discontinue lenalidomide• Dermatology evaluation• Startsupportive measures
Desquamating(blistering) rash	
• Discontinue lenalidomide	
• Discontinue lenalidomide
Any Grade*	
• Dermatology evaluation• Startsupportive measures	
• Dermatology evaluation• Startsupportive measures

Suggested supportive measures :

1. Initiate daily oral antihistamines

Examples

- Loratadine 10mg PO daily
- Cetirizine 10mg PO daily
- Diphenhydramine 25mg PO daily

2. Short-course low-dose oral steroids

Example

- Prednisone 10mg PO x 3 days
- Hydrocortisone 20mg PO QAM, 10mg PO QPM x 3 days

